9.5 Dose Modification

Reduced dose can be administered at the discretion of the treating physician based on individual patient observed toxicity profile and after consultation and agreement by Sponsor Medical Officer.

9.5.1 Dose Modification and Mitigation Plan for Skin Toxicity

- Patients' information will include information about potential skin toxicity.
- Investigators will be trained in skin monitoring and action to findings. Patients should be referred to a dermatologist as deemed relevant.

Skin toxicity should be handled according to the following instructions (based on CTCAE grading):	
Macular-papular skin rash grade 1	Continue dosing of tisotumab vedotin as planned, treat with a potent topical steroid (betamethasone valerate or equivalent) once daily for up to one week, facial areas with a moderate topical steroid (hydrocortisone butyrate 0.1% or equivalent) twice daily for up to one week; thereafter, every other day for a maximum of three weeks.
Macular-papular skin rash grade 2	Postpone dosing of tisotumab vedotin until skin rash has decreased to grade 1, then continue dosing of tisotumab vedotin as planned. Treat the skin rash with a potent topical steroid (betamethasone valerate or equivalent) once daily for up to one week; facial areas with a moderate topical steroid (hydrocortisone butyrate 0.1% or equivalent) twice daily, followed by dosing once every other day for a maximum of three weeks.
Macular-papular skin rash grade ≥ 3	Stop dosing (patient withdrawal), and treat the skin rash with a potent topical steroid (betamethasone valerate or equivalent) once daily for up to one week, followed by dosing once every other day for a maximum of three weeks.
Macular-papular skin rash grade ≥ 3 (covering $\geq 30\%$ of body surface area)	Withdraw patient permanently
Toxic Epidermal Necrolysis, Steven Johnson and cutaneous vasculitis grade ≥ 3	Withdraw patient permanently
Treatment-related bullous dermatitis grade 1 or skin bullae (blister) ≥ 0.5 cm	Withdraw patient permanently

9.5.2 Mitigation Plan for Mucositis

- Patients with CTCAE grade 3 mucositis: hold dosing until mucositis improves to grade 2 and treat according to local practice.
- Withdrawal criteria for mucositis:
 - Patients with CTCAE grade ≥ 4 mucositis: the patient should be withdrawn from treatment.

9.5.3 Dose Modification and Mitigation Plan for Peripheral Neuropathy and Neutropenia

Peripheral neuropathy should be managed using a combination of dose delay and reduction, and should be managed according to the following instructions (based on CTCAE grading):	
New or worsening grade 2 or 3 neuropathy	Hold dose until neuropathy improves to grade ≤ 1 , and then restart at 2/3 of the initial dose until end of trial treatment.
Peripheral neuropathy grade 4	Stop dosing, and the patient should be withdrawn from treatment.
Neutropenia should be managed by dose delays and dose reductions (based on CTCAE grading)	
Neutropenia grade 3 or 4	Dosing should be held for grade 3 or 4 neutropenia until resolution to grade ≤ 2 Growth factor support should be considered for subsequent cycles
Recurrent neutropenia grade 4 despite the use of growth factors	Discontinuation or dose reduction of trial drug to 2/3 of the initial dose until end of trial treatment may be considered after discussion with the Genmab Medical Officer

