8. INVESTIGATIONAL PLAN

8.1 Overall Trial Design and Plan

This is an open-label, multicenter trial to collect long-term safety and efficacy data and to provide ongoing access to tisotumab vedotin for patients with solid tumors who have completed a tisotumab vedotin base trial. Patients demonstrating clinical benefit but who have been withdrawn from the base tisotumab vedotin trials for reasons that are not considered critical and unmanageable for the safety of the patient (as evaluated by the investigator and the sponsor) can also enter this protocol. For patients who received tisotumab vedotin as a single-agent in the base trial, tisotumab vedotin will be given according to the dosing level and schedule administered in the base trial at the time of exiting. Reduced dose can be administered in accordance with the mitigation strategies (Section 9.4 to 9.5.6) or at the discretion of the treating physician based on individual patient observed toxicity profile and after consultation and agreement by the Genmab Medical Officer. Patients will be treated with the tisotumab vedotin dosing regimen followed by the patient in the base trial, until the investigator determines that the patient is no longer benefitting from treatment (i.e., disease progression or unacceptable toxicity has occurred), the trial is terminated by the sponsor, the patient withdraws consent, or for other reasons as defined in this protocol.

In the Treatment Phase, investigators will monitor and assess the patients for response to treatment and for disease progression. Timing and assessments are outlined in the Schedule of Activities (Table 1). Any SAEs, non-serious grade ≥ 2 ocular AEs, non-serious grade ≥ 3 AEs, overdose and/or medication errors, and pregnancies should be reported to the Safety CRO by trial site personnel within 24 hours of their knowledge of the event. All (S)AEs should be reported from the time the patient has signed the ICF until the End-of-Trial (EOT) Visit, or until the patient withdraws consent or starts subsequent anti-cancer therapy, whichever occurs first.

An EOT Visit will occur 30 days after the last administration of trial drug. However, if a patient is unable to return to the site at that time or if the patient is scheduled to start subsequent treatment, this visit should be performed as soon as possible after the last administration of trial drug.

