9.5.4 Dose Modifications and Mitigation Plan for Ocular Adverse Events

Events of conjunctivitis and keratitis have been reported in patients treated with tisotumab vedotin. To prevent occurrence and ensure appropriate handling, events should be prevented and managed as described below.

Ocular toxicity mitigation plan

Ocular toxicity mitigation plan

Preventive measures for all patients:

- Use of preservative-free lubricating eye drops from the start of trial treatment until the end of treatment.
- Avoid use of contact lenses while treated with tisotumab vedotin.
- Use of refrigerator-based eye cooling pads during infusion, e.g. THERA PEARL Eye Mask or similar. To be applied immediately before infusion in accordance with the instructions provided with the eye cooling pads.
- Administration of local ocular vasoconstrictor before infusion (brimonidine tartrate 0.2% eye drops or similar, 3 drops in each eye immediately prior to start of infusion; otherwise to be used in accordance with the product prescribing information). If the patient does not tolerate ocular vasoconstrictors due to adverse reactions, continued treatment with these may be stopped at the discretion of the investigator and following discussion with the Genmab Medical Officer.
- Application of steroid eye drops for 3 days from the day of infusion (dexamethasone 0.1% eye drops or equivalent, 1 drop in each eye 3 times daily for 3 days [first drop to be given before start of infusion], otherwise to be used in accordance with the product prescribing information).

Grading: All ocular events of should be graded according to both:

- Ophthalmological grading based on the objective eye-examination findings performed by the ophthalmologist.
- CTCAE grading system based on National Cancer Institute (NCI) CTCAE version 4.03 ([NCI-CTCAE v4.03, 2010](#)) assessed by the investigator.

Conjunctivitis should be handled according to the following instructions (based on CTCAE grading)

Conjunctivitis grade 1	Hold dosing until the event is managed effectively by topical treatment initiated by the ophthalmologist (according to treatment guidelines below). When the event is managed effectively the patient can be re-treated with the same dose of trial drug as being administered prior to the event onset.

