First occurrence of conjunctivitis grade 2	Hold dosing. Topical treatment should be initiated by the ophthalmologist (according to treatment guidelines below). When the event has improved to grade ≤ 1 , dosing of trial drug can be resumed at a reduced dose (please refer to dose modification scheme below).
Second occurrence of conjunctivitis grade 2	Hold dosing and topical treatment should be initiated by the ophthalmologist (according to treatment guidelines below). When the event is grade ≤ 1 , dosing of trial drug can be resumed at a further reduced dose

Ocular toxicity mitigation plan	
	(please refer to dose modification scheme below).
≥ 3rd occurrence of conjunctivitis grade 2	Hold dosing and topical treatment should be initiated by the ophthalmologist (according to treatment guidelines below). When the event is grade ≤ 1, dosing of trial drug should not be further reduced but resumed at 0.9 mg/kg.
First occurrence of conjunctivitis grade ≥ 3	Hold dosing. Topical treatment should be initiated by the ophthalmologist (according to treatment guidelines below). When the event has improved to grade ≤ 1, dosing of trial drug can be resumed at a reduced dose (please refer to dose modification scheme below).
Second occurrence of conjunctivitis grade ≥ 3 (despite dose reduction)	Permanently discontinue treatment with trial drug.
> 2nd occurrence of conjunctivitis grade > 3	Permanently discontinue treatment with trial drug.
Keratitis should be handled according to the following instructions (based on CTCAE grading)	
First occurrence of keratitis grade ≤ 2	Hold dosing until the event is managed effectively by topical treatment (according to treatment guidelines below) initiated by the ophthalmologist. When the event is ≤ grade 1, dosing of trial drug can be resumed at a reduced dose (please refer to dose modification scheme below).
Second occurrence of keratitis grade ≤ 2	Hold dosing and topical treatment (according to treatment guidelines below) should be initiated by the ophthalmologist. When the event is grade ≤ 1, dosing of trial drug can be resumed at a further reduced dose (please refer to dose modification scheme below).
Third occurrence of keratitis grade ≤ 2 (despite dose reductions)	Permanently discontinue treatment with trial drug.
Keratitis grade ≥ 3	Permanently discontinue treatment with trial drug.
Conjunctival ulceration should be handled according to the following instructions (based on CTCAE grading)	

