If an ophthalmological evaluation reveals fluorescent patches or conjunctival ulceration of any grade	Hold dose until conjunctivitis/conjunctival ulceration is managed effectively by topical treatment (according to treatment guidelines below). When the event is managed effectively, dosing of trial drug can be resumed at a reduced dose (please refer to dose

Ocular toxicity mitigation plan	
	modification scheme below). If symptoms do not stabilize/improve after dose reduction, the patient must permanently discontinue treatment with trial drug.
Other Eye Toxicity should be handled according to the following instructions (based on CTCAE grading)	
Ophthalmological evaluation reveals conjunctival/corneal scarring	Permanently discontinue treatment with trial drug.
Any grade of symblepharon	Permanently discontinue treatment with trial drug.
Any dose delay related to ocular toxicity exceeding 12 weeks	Permanently discontinue treatment with trial drug following discussion with the Genmab Medical Officer.

Treatment guidelines

Ocular symptom	Treatment guideline (The length of treatment should be decided by the local ophthalmologist)
Conjunctivitis: CTCAE grade 1	The local ophthalmologist should prescribe frequent dosing of preservative-free topical steroid drops
Conjunctivitis: CTCAE grade 2	The local ophthalmologist should prescribe frequent dosing (every 2nd hour) of preservative-free topical steroid drops in conjunction with preservative-free antibiotic prophylaxis such as chloramphenicol
Conjunctivitis: CTCAE grade 3	The local ophthalmologist should prescribe frequent dosing (every 2nd hour) of preservative-free topical steroid drops in conjunction with preservative-free antibiotic prophylaxis such as chloramphenicol
Keratitis: CTCAE grade 1	The local ophthalmologist should prescribe frequent dosing of preservative-free topical steroid drops
Keratitis: CTCAE grade 2	The local ophthalmologist should prescribe frequent dosing (every 2nd hour) of preservative-free topical steroid drops in conjunction with preservative-free antibiotic prophylaxis such as chloramphenicol
Conjunctival ulceration: any grade	The local ophthalmologist should prescribe frequent dosing (every 2nd hour) of preservative-free topical steroid drops in conjunction with preservative-free antibiotic prophylaxis such as chloramphenicol

Dose modification scheme:

Previous dose of tisotumab vedotin	Reduced dose of tisotumab vedotin
---	--

2.0 mg/kg	1.3 mg/kg
1.3 mg/kg	0.9 mg/kg

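### Protocol 9.5.3 bases the restart dose after neuropathy on an undefined initial dose, so a patient already reduced for ocular events gets no real cut, or a 48% increase

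*Protocol*

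**What the plan says.** Patients do not all start this trial at the same dose. Protocol 8.1 states that, for patients who had it as a single agent, "tisotumab vedotin will be given according to the dosing level and schedule administered in the base trial at the time of exiting". Table 2 in 9.2 and SAP 4.5 agree: 2.0 mg/kg, or the reduced dose carried over from the base trial. During this trial, 9.5.4 can lower the dose for ocular events from 2.0 to 1.3 and from 1.3 to 0.9 mg/kg, with no reduction below 0.9.

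The neuropathy rule in 9.5.3 opens with its intent: "Peripheral neuropathy should be managed using a combination of dose delay and reduction". For new or worsening grade 2 or 3 events, dosing is held until grade 1 or lower, and the site is then to "restart at 2/3 of the initial dose until end of trial treatment". The row for recurrent grade 4 neutropenia offers discontinuation or "dose reduction of trial drug to 2/3 of the initial dose until end of trial treatment", but only as something to consider after discussion with the sponsor's medical officer. The neuropathy row carries no such condition.

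Neither document says which dose is the initial one. Section 9.5.4 uses different terms when it means the dose currently being given: the grade 1 conjunctivitis row refers to the "same dose of trial drug as being administered prior to the event onset", and the dose scheme has the column header "Previous dose of tisotumab vedotin".

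**The concern.** In a trial where everyone starts at one dose and is reduced for one reason only, two-thirds of the initial dose is always a reduction. Neither condition holds here. This is a rollover trial with carried-over doses, and a second toxicity rule can lower the dose independently. A restart fixed to a starting dose can then land at or above the dose the patient was receiving when the neuropathy appeared.

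Neuropathy is an adverse event of special interest (11.1.3). Grade 2 or higher neuropathy bars entry (8.5.2), so this row governs neuropathy that develops or worsens during long-term treatment, which is what the primary objective is about. Followed literally, it could give a patient at the ocular floor a higher dose straight after grade 2 or 3 neuropathy, and undo the reduction made for the eyes. It also blurs what counts as a correct dose: 11.3.2 defines overdose relative to the dose the protocol specifies, and for some patients the row specifies two different doses.

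**Working it through.** **Inputs**

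- Unreduced dose 2.0 mg/kg: Protocol Table 2, SAP 4.5.
- Dose at entry: base-trial exit dose, Protocol 8.1.
- Ocular scheme 2.0 → 1.3 → 0.9 mg/kg, floor 0.9: Protocol 9.5.4.
- Restart factor 2/3: Protocol 9.5.3.
- Assumption, needed only where the initial dose is read as the first base-trial dose: that dose was 2.0 mg/kg.

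**The plan's own figures first.** 2/3 × 2.0 = 1.333, and the scheme states 1.3. 2/3 × 1.3 = 0.867, and the scheme states 0.9. Both ocular steps are two-thirds of the previous dose to one decimal (exact ratios 1.3/2.0 = 0.65 and 0.9/1.3 = 0.69).

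**Formulas.** Restart dose R = 2/3 × initial dose. Change at restart = R / current dose − 1.

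**Patient who entered at 2.0 mg/kg.** The initial dose is 2.0 on either reading, so R = 1.333 mg/kg.

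| Current dose (mg/kg) | Change, R = 1.333 | Change, R rounded to 1.3 |
|---|---|---|
| 2.0 | −33.3% | −35.0% |
| 1.3 | +2.6% | 0% |
| 0.9 | +48.1% | +44.4% |

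The rule does what its heading says only when the patient is still on 2.0 mg/kg. At an assumed body weight of 70 kg, the last row goes from 0.9 × 70 = 63 mg to 1.333 × 70 = 93 mg.

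**Patient who entered already reduced.** The result depends on the reading.

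| Entry / current dose (mg/kg) | Initial = first dose in this trial | Initial = first base-trial dose |
|---|---|---|
| 1.3 / 1.3 | 0.867 (−33.3%) | 1.333 (+2.6%) |
| 1.3 / 0.9 | 0.867 (−3.7%) | 1.333 (+48.1%) |
| 0.9 / 0.9 | 0.600 (−33.3%) | 1.333 (+48.1%) |

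For entry at 0.9 mg/kg the two readings differ by a factor of 1.333/0.600 = 2.2, and the lower one falls below the 0.9 mg/kg floor that 9.5.4 sets for ocular reductions.

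**With the restart tied to the previous dose through the existing scheme:** 2.0 → 1.3 is −35%, 1.3 → 0.9 is −31%, and 0.9 stays at 0.9 or treatment stops. The dose cannot rise.

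**The case against.** The strongest reply is that no site would raise the dose. Wherever the documents discuss departing from the assigned dose (Protocol 6.4, 8.1, Table 2 and 9.5; SAP 4.5), they speak of reduction. Nothing provides for re-escalation, and the rule's own heading points downwards. Section 9.5 also lets the physician choose a lower dose with the medical officer's agreement. Grade 3 neuropathy would reach the Safety CRO within 24 hours (11.3.1) and be evaluated by the sponsor on receipt (11.8).

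Much of this is fair, and it limits the practical risk. It does not repair the row. The latitude in 9.5 is permissive and leaves the specific instruction unchanged, and the 24-hour route does not cover non-serious grade 2 neuropathy. A site that declines to raise the dose is correcting the text, and the text does not say what dose to give instead.

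Three narrower replies also have weight.

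- The clause runs to the end of trial treatment, which favours the first dose in this trial as the reference. On that reading the 48% increase is confined to a patient who entered at 2.0 mg/kg, had two dose steps down here, and then developed neuropathy. That case remains, and it needs no choice of reading.
- The 2.6% is rounding: in the protocol's own scheme 1.3 mg/kg is two-thirds of 2.0. A single target level that does not stack on earlier reductions is a coherent design. If that was intended, the row should say so, because its heading calls for a reduction.
- Stacking a neuropathy step on an ocular step is partly a matter of dosing policy. That argues for offering the sponsor a minimum fix, not for leaving the row as it is.

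**Conclusion.** The point holds and is minor. Read literally, the neuropathy row gives a result contrary to its stated purpose for a patient who entered at 2.0 mg/kg and was then reduced in this trial: effectively no cut from 1.3 mg/kg, and a rise of 48% (44% rounded) from 0.9 mg/kg. For patients who enter reduced, the restart dose is ambiguous; entry at 0.9 mg/kg gives 0.60 or 1.33 mg/kg. The base-trial reading assumes a 2.0 mg/kg start. The documents do not say how many of the roughly 25 expected patients enter below 2.0 mg/kg or are reduced here. Endpoints are only listed, so no test or estimate is affected.

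A reader might infer three stronger things that the documents do not support.

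- That the ocular dose rules fail for reduced patients too. They do not: the 9.5.4 scheme is keyed to the previous dose and has a footnote for patients already at 0.9 mg/kg.
- That the share of entry and current dose combinations with a rise measures the risk. The frequencies of those combinations are unknown, and most of the rises depend on the weaker, base-trial reading.
- That 9.5.3 and 9.5.4 must share one starting point, because 9.5.4 does not say whether base-trial ocular events count towards its occurrence-based stops. A reference dose and an event count are different quantities. The ocular count needs a clarification and nothing more.

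**What to change.** In the neuropathy row of 9.5.3, and in the optional neutropenia row, replace the reference to the initial dose with the dose given immediately before the event, and add that the restart dose must never exceed it.

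One way is a single step down the existing 9.5.4 scheme (2.0 to 1.3, 1.3 to 0.9 mg/kg). At 0.9 mg/kg the sponsor's medical officer would decide between continuing at that dose and stopping. The steps are already about two-thirds, so the intended size of the cut is kept. If the sponsor prefers one non-stacking level, the minimum fix is the cap at the pre-event dose, with a statement that a patient already at that level or below is not reduced further.

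As a separate clarification, one sentence in 9.5.4 could say whether base-trial occurrences count.

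The cost is a wording change to two rows, plus the optional sentence. No new procedure, data field or listing is needed. The trade-off with the stepwise version is clinical: a patient at 1.3 mg/kg would go to 0.9 mg/kg after neuropathy, with possible loss of activity. At 0.9 mg/kg, continuing is not a reduction, which is why that decision goes to the medical officer.

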9.5.4 Dose Modifications and Mitigation Plan for Ocular Adverse Events

Events of conjunctivitis and keratitis have been reported in patients treated with tisotumab vedotin. To prevent occurrence and ensure appropriate handling, events should be prevented and managed as described below.

Ocular toxicity mitigation plan

Ocular toxicity mitigation plan

Preventive measures for all patients:

- Use of preservative-free lubricating eye drops from the start of trial treatment until the end of treatment.
- Avoid use of contact lenses while treated with tisotumab vedotin.
- Use of refrigerator-based eye cooling pads during infusion, e.g. THERA PEARL Eye Mask or similar. To be applied immediately before infusion in accordance with the instructions provided with the eye cooling pads.
- Administration of local ocular vasoconstrictor before infusion (brimonidine tartrate 0.2% eye drops or similar, 3 drops in each eye immediately prior to start of infusion; otherwise to be used in accordance with the product prescribing information). If the patient does not tolerate ocular vasoconstrictors due to adverse reactions, continued treatment with these may be stopped at the discretion of the investigator and following discussion with the Genmab Medical Officer.
- Application of steroid eye drops for 3 days from the day of infusion (dexamethasone 0.1% eye drops or equivalent, 1 drop in each eye 3 times daily for 3 days [first drop to be given before start of infusion], otherwise to be used in accordance with the product prescribing information).

Grading: All ocular events of should be graded according to both:

- Ophthalmological grading based on the objective eye-examination findings performed by the ophthalmologist.
- CTCAE grading system based on National Cancer Institute (NCI) CTCAE version 4.03 ([NCI-CTCAE v4.03, 2010](#)) assessed by the investigator.

Conjunctivitis should be handled according to the following instructions (based on CTCAE grading)

Conjunctivitis grade 1	Hold dosing until the event is managed effectively by topical treatment initiated by the ophthalmologist (according to treatment guidelines below). When the event is managed effectively the patient can be re-treated with the same dose of trial drug as being administered prior to the event onset.
First occurrence of conjunctivitis grade 2	Hold dosing. Topical treatment should be initiated by the ophthalmologist (according to treatment guidelines below). When the event has improved to grade ≤ 1 , dosing of trial drug can be resumed at a reduced dose (please refer to dose modification scheme below).
Second occurrence of conjunctivitis grade 2	Hold dosing and topical treatment should be initiated by the ophthalmologist (according to treatment guidelines below). When the event is grade ≤ 1 , dosing of trial drug can be resumed at a further reduced dose

Ocular toxicity mitigation plan	
	(please refer to dose modification scheme below).
≥ 3rd occurrence of conjunctivitis grade 2	Hold dosing and topical treatment should be initiated by the ophthalmologist (according to treatment guidelines below). When the event is grade ≤ 1, dosing of trial drug should not be further reduced but resumed at 0.9 mg/kg.
First occurrence of conjunctivitis grade ≥ 3	Hold dosing. Topical treatment should be initiated by the ophthalmologist (according to treatment guidelines below). When the event has improved to grade ≤ 1, dosing of trial drug can be resumed at a reduced dose (please refer to dose modification scheme below).
Second occurrence of conjunctivitis grade ≥ 3 (despite dose reduction)	Permanently discontinue treatment with trial drug.
> 2nd occurrence of conjunctivitis grade > 3	Permanently discontinue treatment with trial drug.
Keratitis should be handled according to the following instructions (based on CTCAE grading)	
First occurrence of keratitis grade ≤ 2	Hold dosing until the event is managed effectively by topical treatment (according to treatment guidelines below) initiated by the ophthalmologist. When the event is ≤ grade 1, dosing of trial drug can be resumed at a reduced dose (please refer to dose modification scheme below).
Second occurrence of keratitis grade ≤ 2	Hold dosing and topical treatment (according to treatment guidelines below) should be initiated by the ophthalmologist. When the event is grade ≤ 1, dosing of trial drug can be resumed at a further reduced dose (please refer to dose modification scheme below).
Third occurrence of keratitis grade ≤ 2 (despite dose reductions)	Permanently discontinue treatment with trial drug.
Keratitis grade ≥ 3	Permanently discontinue treatment with trial drug.
Conjunctival ulceration should be handled according to the following instructions (based on CTCAE grading)	
If an ophthalmological evaluation reveals fluorescent patches or conjunctival ulceration of any grade	Hold dose until conjunctivitis/conjunctival ulceration is managed effectively by topical treatment (according to treatment guidelines below). When the event is managed effectively, dosing of trial drug can be resumed at a reduced dose (please refer to dose

Ocular toxicity mitigation plan	
	modification scheme below). If symptoms do not stabilize/improve after dose reduction, the patient must permanently discontinue treatment with trial drug.
Other Eye Toxicity should be handled according to the following instructions (based on CTCAE grading)	
Ophthalmological evaluation reveals conjunctival/corneal scarring	Permanently discontinue treatment with trial drug.
Any grade of symblepharon	Permanently discontinue treatment with trial drug.
Any dose delay related to ocular toxicity exceeding 12 weeks	Permanently discontinue treatment with trial drug following discussion with the Genmab Medical Officer.

Treatment guidelines

Ocular symptom	Treatment guideline (The length of treatment should be decided by the local ophthalmologist)
Conjunctivitis: CTCAE grade 1	The local ophthalmologist should prescribe frequent dosing of preservative-free topical steroid drops
Conjunctivitis: CTCAE grade 2	The local ophthalmologist should prescribe frequent dosing (every 2nd hour) of preservative-free topical steroid drops in conjunction with preservative-free antibiotic prophylaxis such as chloramphenicol
Conjunctivitis: CTCAE grade 3	The local ophthalmologist should prescribe frequent dosing (every 2nd hour) of preservative-free topical steroid drops in conjunction with preservative-free antibiotic prophylaxis such as chloramphenicol
Keratitis: CTCAE grade 1	The local ophthalmologist should prescribe frequent dosing of preservative-free topical steroid drops
Keratitis: CTCAE grade 2	The local ophthalmologist should prescribe frequent dosing (every 2nd hour) of preservative-free topical steroid drops in conjunction with preservative-free antibiotic prophylaxis such as chloramphenicol
Conjunctival ulceration: any grade	The local ophthalmologist should prescribe frequent dosing (every 2nd hour) of preservative-free topical steroid drops in conjunction with preservative-free antibiotic prophylaxis such as chloramphenicol

Dose modification scheme:

Previous dose of tisotumab vedotin	Reduced dose of tisotumab vedotin
---	--

2.0 mg/kg	1.3 mg/kg
1.3 mg/kg	0.9 mg/kg
0.9 mg/kg	0.9 mg/kg*

**If the patient is already being treated with tisotumab vedotin (HuMax-TF-ADC) 0.9 mg/kg every 3rd week, the dose of tisotumab vedotin (HuMax-TF-ADC) should not be reduced further.*

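### A second grade 1 keratitis meets the written condition for ending its dosing hold at onset, while the other three hold rows open to grade 1 require effective management

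*Protocol*

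**What the plan says.** The ocular mitigation plan in Protocol Section 9.5.4 gives one row per event type, grade and occurrence. Keratitis of grade 1 or 2 has three rows.

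- **First occurrence:** "Hold dosing until the event is managed effectively by topical treatment (according to treatment guidelines below) initiated by the ophthalmologist". Dosing may then resume at a reduced dose once the event is grade 1 or below.
- **Second occurrence** ("Second occurrence of keratitis grade ≤ 2"): dosing is held and topical treatment "should be initiated by the ophthalmologist. When the event is grade ≤ 1, dosing of trial drug can be resumed" at a further reduced dose.
- **Third occurrence:** treatment stops permanently.

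Grade 1 keratitis is an expected entry to these rows, because the treatment guidelines in the same section list "Keratitis: CTCAE grade 1" separately and prescribe steroid drops for it.

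The conjunctival ulceration row, which covers any grade, reads "Hold dose until conjunctivitis/conjunctival ulceration is managed effectively by topical treatment". The conjunctivitis grade 1 row also holds dosing until the event is managed effectively.

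**The concern.** A hold needs a condition that is not met when it starts. For a second keratitis at grade 2, falling to grade 1 or below is such a condition. At grade 1 it is met on the day the event is found. Read literally, the site must hold dosing and have drops started, but the row does not require the drops to have worked before the next infusion.

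The strictness also runs the wrong way. The recurrence is the last keratitis before permanent discontinuation, yet its written release rule is weaker than that for a first keratitis or a grade 1 conjunctivitis. Sites could apply the hold differently, in a class of event that Section 11.1.3 names as being of special interest.

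**Working it through.** The plan states no figure on this point. The check is to list every row in Section 9.5.4 that holds dosing and compare the grade at entry with the condition that ends the hold.

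| Hold row | Grade at entry | Condition to resume | Met by a grade 1 event at onset? |
|---|---|---|---|
| Conjunctivitis grade 1 | 1 | Managed effectively | No |
| Conjunctivitis grade 2, first | 2 | Grade ≤ 1 | Cannot enter at grade 1 |
| Conjunctivitis grade 2, second | 2 | Grade ≤ 1 | Cannot enter at grade 1 |
| Conjunctivitis grade 2, third or later | 2 | Grade ≤ 1 | Cannot enter at grade 1 |
| Conjunctivitis grade ≥ 3, first | ≥ 3 | Grade ≤ 1 | Cannot enter at grade 1 |
| Keratitis grade ≤ 2, first | 1 or 2 | Managed effectively, and grade ≤ 1 | No |
| Keratitis grade ≤ 2, second | 1 or 2 | Grade ≤ 1 | **Yes** |
| Conjunctival ulceration | Any | Managed effectively | No |

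There are eight hold rows, and four admit grade 1. Of those four, three require effective management and one does not. In the four rows that cannot be entered at grade 1, the grade ≤ 1 condition is a real improvement. The second-keratitis row is worded almost like the second conjunctivitis grade 2 row. A drafting carry-over is therefore plausible, though the documents do not say so.

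**Does the further dose reduction stand in for the missing condition?** The dose scheme in Section 9.5.4 runs 2.0 → 1.3 → 0.9 → 0.9 mg/kg. For a patient entering at 2.0 mg/kg:

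- With no other ocular reduction, the first keratitis gives 1.3 and the second gives 0.9. The cut at the second is (1.3 − 0.9)/1.3 = 30.8%.
- With one earlier ocular step in this trial, for example under "First occurrence of conjunctivitis grade 2", the dose is 1.3 before the first keratitis and 0.9 after it. The second keratitis leaves it at 0.9, a cut of (0.9 − 0.9)/0.9 = 0%.

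The second route does not depend on whether occurrences in the base trial are counted. These cuts come from the dose scheme and would be the same under corrected wording. They show only that the reduction cannot be relied on as a substitute.

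**Does the cycle length supply a hold?** Infusions fall on Day 1 of a 21-day cycle (Section 9.2). An event found the day after an infusion has 21 − 1 = 20 days on drops before the next scheduled dose. If the ± 7 days in Table 1 is read as applying to cycle length, which is an assumption, the range is 14 − 1 = 13 to 28 − 1 = 27 days. For an event found on Day 1 before the infusion, the row states no minimum.

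**The case against.** The best reply is that the gap depends on a very literal reading. The row gives a sequence: hold, treat, then decide. If grade 1 at onset released the hold, the instruction to hold would do nothing for a grade that the row expressly includes, so a sensible site would wait for a response to treatment. The missing phrase is also undefined in the protocol, so adding it brings in a clinical judgment rather than a threshold.

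Safeguards remain as well:

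- Resumption is permitted, not required.
- The dose falls further unless it is already 0.9 mg/kg, whereas a grade 1 conjunctivitis resumes at the same dose.
- Ocular symptoms must be reviewed by an ophthalmologist, preferably within 72 hours and at latest within a week (Section 10.1.7).
- The ophthalmologist sets the length of topical treatment.
- The physician may reduce the dose for individual toxicity with the sponsor's agreement (Section 9.5).
- The investigator may stop treatment for safety (Section 8.5.3.1).

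All of this is accurate, and it limits the practical effect. None of it sets a condition for ending the hold. The protocol wrote the clinical judgment into the three comparable rows, and two of those, first keratitis and ulceration, also call for a dose reduction. No reason is given for leaving it out of this one.

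**Conclusion.** The concern holds, as a minor point. One of the four hold rows that admit grade 1 has a release condition that a grade 1 event meets at onset, and nothing elsewhere in the protocol or SAP supplies another. The textual finding is firm and rests on no assumption beyond reading the rows as written.

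The consequence is narrow. It concerns a second keratitis that is grade 1 and present when an infusion is due. Grade 2 events in the same row are handled coherently. How often the exposed case would arise cannot be judged, because the documents give no event counts and expect about 25 patients. That sites would differ in practice is an inference. No endpoint or analysis changes, since Section 12.2 provides only for listings.

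**What to change.** Open the second-occurrence row with the clause already used for the first: "Hold dosing until the event is managed effectively by topical treatment (according to treatment guidelines below) initiated by the ophthalmologist". Then permit resumption, at the further reduced dose, only when the event is both managed effectively and grade 1 or below. This matches the first-keratitis row and gives all four rows open to grade 1 the effective-management requirement. It does not define that term. The conjunctivitis rows and the eCRF need no change.

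First check whether GEN701 and GEN702 carry the same row. If they do, change it there too: Amendment 2 was prepared to align this protocol with them, and a change here alone would break that alignment.

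The cost is one table row, which can go into the next amendment with the written regulatory and ethics approval that Section 15.2 requires. Some second grade 1 events may be held longer. That time counts toward the limit in the row "Any dose delay related to ocular toxicity exceeding 12 weeks", which leads to permanent discontinuation after discussion with the sponsor's medical officer. The first-keratitis row already accepts the same cost.
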